# Table 11Study groups, treatment and epochs foreseen in the study (PoPepochs)

| Study               | Number of | Age           | Epochs
(Blinding)           |                        |                                     |
|---------------------|-----------|---------------|--------------------------------|------------------------|-------------------------------------|
| Groups              | subjects  | (Min-Max)     | Treatment name                 | PoP screening
(N/A) | PoP vaccination
(observer-blind) |
| Group 5a
Vaccine | 250*      | 18 - 64 years | Sa-5Ag full dose
adjuvanted | •                      | •                                   |
| Group 5b
Placebo | 250*      | 18 - 64 years | Placebo                        | •                      | •                                   |

N/A = Not Applicable

\*Design of the study is event driven and it can be only estimated that approximately 250 to 300 subjects per study group may be needed. Enrolment may continue until 27 events are reached.

- **Control:** placebo control
- Vaccination schedule(s):
  - **Group 5a Vaccine:** A series of 2 doses of *S. aureus* candidate vaccine (Sa-5Ag full dose adjuvanted) given approximately 2 months apart (Days 1 and 61)
  - **Group 5b Placebo:** A series of 2 doses of placebo (saline) given approximately 2 months apart (Days 1 and 61)
- **Treatment allocation:** randomised, subjects will be allocated to a study group using an automated, electronic system (SBIR).
- **Blinding:** not applicable for the screening epoch, and the vaccination epoch is observer-blind

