For each group in the dose-escalation safety lead-in, a staggered enrolment of 8 subjects is planned as follows: 1 vaccinated subject + 1 subject receiving placebo (sentinel subjects) followed by 5 vaccinated subjects + 1 subject receiving placebo after safety assessment of safety data collected up to Day 8. The 2 sentinel subjects in each group should be vaccinated on 2 different days.

The fourth group (Full dose adjuvanted) will receive a second vaccine/placebo dose with an interval of approximately 2 months and subjects of all the groups will be followed until study end (i.e. for 12 months after last vaccination for each subject).

The investigator is not permitted to start the administration of Dose 1 for the next group and Dose 2 in the fourth group until receipt of the favourable outcome of the safety evaluation.

During the whole study period, if the investigator becomes aware of a holding rule being met, he/she will suspend vaccination and will inform GSK immediately (e.g. in case of death or any life-threatening SAEs). Please, refer to section 8.6 of the study protocol for detailed description of holding rules and safety monitoring.

208833 (STAPH AUREUS BIOCONJ-001 STG) Statistical Analysis Plan Amendment 5

PoP in subjects with recent S. aureus SSTI

Figure 3 Study design overview PoP in subjects with a recent S. aureus SSTI

Note: CDISC is not calculating with Day 0, i.e. interval between Day -30 and Day 1 is 30 days.

208833 (STAPH AUREUS BIOCONJ-001 STG) Statistical Analysis Plan Amendment 5

a/b = vaccine/placebo SE = Safety evaluation by iSRC (unblinded), for details refer to Section 8.6.6 in the Study Protocol PoP = Proof of Principle SSTI = Skin and Soft Tissue Infection Rando = Randomization Vac = Vaccine Plac = Placebo M = Month V = Vaccination

BS-S = Blood Sample for Safety evaluation

• Vaccination schedule(s):

- **Group 5a Vaccine:** A series of 2 doses of *S. aureus* candidate vaccine (Sa-5Ag full dose adjuvanted) given approximately 2 months apart (Days 1 and 61)
- **Group 5b Placebo:** A series of 2 doses of placebo (saline) given approximately 2 months apart (Days 1 and 61)

• Safety monitoring:

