5.5.2. Additional considerations

5.5.2.1. Analysis of solicited AEs

The analysis of solicited AEs will be performed on the Solicited safety set and Solicited safety set 30 m.

The following local AEs will be solicited for 7 days after each vaccination:

208833 (STAPH AUREUS BIOCONJ-001 STG)

Statistical Analysis Plan Amendment 5

Local AE	Grading	Collection period
Pain at injection site	0: None	Day 1-Day 7
	1: Mild	Day 61-Day 67
	2: Moderate	
	3: Severe	
Redness at injection site	0: < 25 mm diameter	Day 1-Day 7
	1: \geq 25 mm to \leq 50 mm diameter	Day 61-Day 67
	2: > 50 mm to \leq 100 mm diameter	
	3: > 100 mm diameter	
Swelling at injection site	0: < 25 mm diameter	Day 1-Day 7
	1: \geq 25 mm to \leq 50 mm diameter	Day 61-Day 67
	2: > 50 mm to \leq 100 mm diameter	
	3: > 100 mm diameter	

Table 7Solicited local adverse events and their grading:

For the grading definition of Pain please refer to Table 34 of the study protocol.

The percentage of subjects with at least one local solicited AE reported in e-diary, within 7 days period after each dose, will be tabulated by group together with the exact 95% CI [Clopper, 1934]. Similarly, the percentage of doses followed by at least one local solicited AE will be tabulated together with the exact 95% CIs within each group. The same tabulation will be done for grade 3 solicited local AEs.

The following general AEs will be solicited for 7 days after each vaccination:

Table 8 Solicited general adverse events and their grading:

General AE	Grading	Collection period
Headache	0: None 1: Mild 2: Moderate 3: Severe	Day 1-Day 7 Day 61-Day 67
Fatigue	0: None 1: Mild 2: Moderate 3: Severe	Day 1-Day 7 Day 61-Day 67
Nausea	0: None 1: Mild 2: Moderate 3: Severe	Day 1-Day 7 Day 61-Day 67
Vomiting	0: None 1: Mild 2: Moderate 3: Severe	Day 1-Day 7 Day 61-Day 67
Diarrhoea	0: None 1: Mild 2: Moderate 3: Severe	Day 1-Day 7 Day 61-Day 67
Abdominal pain	0: None 1: Mild 2: Moderate 3: Severe	Day 1-Day 7 Day 61-Day 67

208833 (STAPH AUREUS BIOCONJ-001 STG) Statistical Analysis Plan Amendment 5

General AE	Grading	Collection period
Myalgia*	0: None 1: Mild 2: Moderate 3: Severe	Day 1-Day 7 Day 61-Day 67
Shivering*	0: None 1: Mild 2: Moderate 3: Severe	Day 1-Day 7 Day 61-Day 67
Fever	0: < 38°C 1: 38°C to <39°C 2: ≥ 39.0°C to ≤40°C 3: > 40.0°C	Day 1-Day 7 Day 61-Day 67

*This AE will be collected as solicited during the PoP epoch (only for group 5)

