For the grading definition of general solicited AEs please refer to Table 34 of the study protocol.

The percentage of subjects with at least one general solicited AE reported in e-diary within 7 days, after each dose will be tabulated by group together with the exact 95% CI.

Similarly, the percentage of doses followed by at least one general solicited AE will be tabulated together with the exact 95% CIs within each group.

The same tabulation will be done for grade 3 solicited general AEs.

The percentages of subjects reporting each individual local and general solicited AE by maximum grading during the solicited follow-up period (i.e., day of vaccination and six subsequent days after each vaccination) will be tabulated with exact 95% CIs after each dose and overall by group. The percentages of doses followed by each individual solicited local and general AE by maximum grading will be tabulated overall by group with exact 95% CIs [Clopper, 1934].

For solicited symptoms, missing or unevaluable measurements will not be replaced. Therefore, the analysis of the solicited symptoms will include only subjects/doses with documented safety data (i.e., symptom screen/sheet completed).

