5.5.2.2. Analysis of unsolicited AEs, SAE and pIMD

The analysis of unsolicited AEs will be performed on the Unsolicited safety set.

All the unsolicited adverse events occurring during the study, judged either as related or not related to vaccination by the investigator, will be recorded.

The original verbatim terms used by investigators to identify adverse events in the e-CRFs will be mapped to preferred terms using the MedDRA dictionary. The unsolicited adverse events will then be grouped by MedDRA preferred terms into frequency tables according to system organ class. Adverse events judged by the investigator as at least possibly related to study vaccine will be summarized by vaccine group, according to System Organ Class (SOC) and Preferred Term (PT) within SOC. When an unsolicited adverse event occurs more than once for a subject, the maximal severity and strongest relationship to the vaccine group will be counted (specifically, for dose-escalation safety lead-in).

The percentage of subjects with at least one report of unsolicited AE classified by the MedDRA during a 30-day follow-up period after each dose (i.e. day of injection and the 29 subsequent days) will be tabulated with exact 95% CI for each group. The same tabulation will be performed by severity, by vaccination and for unsolicited AEs with a relationship to vaccination.

SAEs, deaths, pIMDs and AEs leading to withdrawal reported during the entire study will be tabulated (from Day 1 until study termination) and listed.

In addition, SAEs related to study participation or concurrent GSK medication/vaccine reported from inform consent signed until entire study duration will be also listed.

Incidence of COVID-19 reported as an unsolicited AE and SAE will be tabulated with exact 95% CI for each group.

A summary of COVID-19 assessments throughout the study will be tabulated for each group.

This study foresees one injection in groups 1-3 and two injections (i.e., two vaccinations) for each subject in groups 4 and 5, and thus unsolicited AEs summary tables will be presented overall and by period of onset and will include frequency distributions of the different adverse events.

Number and percentage of subjects with the following AEs will be computed:

Onset between the day of each injection and the 29 subsequent days after each vaccination:

- Any AE (overall)
- Any AE by vaccination
- Any AE by severity (overall) (only Grade 3 severity for dose-escalation safety leadin)

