6. ANALYSIS INTERPRETATION

Except for analysis on efficacy objectives, with predefined success criteria and an appropriate type I error control, comparative analyses are descriptive with the aim to characterize the difference between groups.

With respect to confirmatory analyses on efficacy objectives the interpretation will be done in a hierarchical manner.

After the final analysis for the first hypothesis a sequential procedure will be used in order to control the overall type I error for the efficacy objective: starting from the first

208833 (STAPH AUREUS BIOCONJ-001 STG) Statistical Analysis Plan Amendment 5

hypothesis on the efficacy after the second dose, the second hypothesis on the efficacy after the first dose will be tested only if the efficacy after two doses will be demonstrated.

Figure 4 Sequence for evaluating both efficacy objectives in order to control the overall type I error below 7.5% (one-sided) and the power equal to 80%

*All subjects who experience an SSTI recurrence at least two weeks after the second dose. If a subject experiences an event after the first and before the second dose the case will be not considered as first event after the second dose. If a subject has an event after the first and another after the second dose, only the case after the second dose will be considered as first event after the second dose.

**The adjusted alpha for this hypothesis can only be given at the time of analysis as the adjustment is dependent on the alpha spent at the interim analysis.

***All subjects who experience an SSTI recurrence at least two weeks after the first dose.

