10.1.5. Statistical methodology

10.1.5.1. Exact confidence intervals around proportions

The exact confidence intervals around within-group proportions are derived using the method of Clopper and Pearson [Clopper, 1934].

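### Group 5 solicited-reaction percentages of doses get Clopper-Pearson intervals that ignore two doses coming from one subject, so they are too narrow if a subject's two reactions are positively correlated

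*SAP*

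**What the plan says.** SAP 5.5.2.1, under the additional safety considerations, first plans percentages of subjects with a solicited reaction after each dose. It then adds a second set of rows with doses as the denominator. For local reactions, "the percentage of doses followed by at least one local solicited AE will be tabulated together with the exact 95% CIs within each group". Any general reaction and grade 3 reactions are treated likewise. For single reactions, "percentages of doses followed by each individual solicited local and general AE by maximum grading will be tabulated overall by group with exact 95" per cent intervals.

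The interval method is fixed in SAP 10.1.5.1: "The exact confidence intervals around within-group proportions are derived using the method of Clopper and Pearson". SAP 9.2, which would hold any study-specific statistical method, is marked not applicable.

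SAP 5.5.2.2 gives the number of doses per subject: "This study foresees one injection in groups 1-3 and two injections (i.e., two vaccinations) for each subject in groups 4 and 5". Two is a maximum, because under SAP 5.5.2.1 "the analysis of the solicited symptoms will include only subjects/doses with documented safety data".

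On size, the footnote to Table 11 in Protocol 5.2.2 says of Group 5 that "it can be only estimated that approximately 250 to 300 subjects per study group may be needed". Each lead-in group, including Group 4, is enrolled as "1 vaccinated subject + 1 subject receiving placebo (sentinel subjects) followed by 5 vaccinated subjects + 1 subject receiving placebo" (SAP 3), which makes 6 vaccine and 2 placebo subjects.

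**The concern.** Clopper-Pearson inverts a binomial distribution, so it needs independent trials. Two doses given to the same person are not obviously independent: the product is the same and the same person rates the symptoms. If someone who reacts to dose 1 is more likely to react to dose 2, then 500 doses from 250 subjects carry less information than 500 doses from 500 subjects. An interval computed on 500 is then too short for its 95% label.

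The issue arises only where the two doses are pooled. Pooling is explicit for the single-reaction rows (overall by group). It is the natural reading, though not spelled out, for the any-local and any-general rows.

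What is at stake is the labelling of descriptive reactogenicity intervals that will appear in the study report. The point estimates do not change.

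**Working it through.** The documents state no width, coverage or precision for these rows, so there is no planned figure to reproduce. The check is the true coverage of the planned interval.

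**Inputs from the documents.** Unit of analysis: doses (SAP 5.5.2.1). Method: two-sided 95% Clopper-Pearson (SAP 10.1.5.1). Up to 2 doses per subject in Group 5 (SAP 5.5.2.2). Arm size 250 to 300 (Protocol Table 11), hence up to 2 × 250 = 500 doses in an arm of 250.

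**Assumptions.** Reaction rate p, equal at both doses, and within-subject correlation r. The documents give neither, so both are varied.

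**Model.** With q = 1 − p, each subject has
- both doses with a reaction: p² + rpq
- exactly one: 2pq(1 − r)
- neither: q² + rpq

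Convolving this over 250 subjects gives the exact distribution of the event count. Coverage is the probability that Clopper-Pearson on 500 doses contains p.

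| Rate p | r = 0 | 0.1 | 0.3 | 0.5 |
|---|---|---|---|---|
| 5% | 96.0% | 95.0% | 92.9% | 90.7% |
| 10% | 96.3% | 95.4% | 93.3% | 91.2% |
| 30% | 95.5% | 94.4% | 92.1% | 89.8% |
| 50% | 95.6% | 94.5% | 92.3% | 90.0% |
| 60% | 95.5% | 94.4% | 92.2% | 89.9% |

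**Rare events.** Coverage is irregular because counts are discrete. At r = 0.3 it is 97.2% for a 0.5% rate, 96.0% for 1%, 92.8% for 1.5% and 95.4% for 2%.

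**Sensitivity at r = 0.1 / 0.3 / 0.5.**
- 300 subjects, 30% rate: 94.4 / 92.1 / 89.8%.
- Second dose missing in 50 of 250, 30% rate: 94.6 / 92.5 / 90.5%.
- Rates of 20% and 40% at the two doses: 95.0 / 92.9 / 90.7%.

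**Effect on the limits.** For two doses per subject the variance of the pooled percentage is pq(1 + r)/500, so the design effect is 1 + r and the effective number of doses is 500/(1 + r). Clopper-Pearson at a 30% rate gives:

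| r | Effective doses | 95% limits | Shift of lower / upper limit (points) |
|---|---|---|---|
| 0 (as planned) | 500 | 26.0-34.2% | – |
| 0.1 | 454.5 | 25.8-34.4% | 0.2 / 0.2 |
| 0.3 | 384.6 | 25.5-34.9% | 0.6 / 0.6 |
| 0.5 | 333.3 | 25.1-35.2% | 0.9 / 1.0 |

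**Group 4.** With 6 subjects (12 doses), mean coverage over rates of 2-98% is 96.2% at r = 0.3 and 94.8% at r = 0.5. With 2 subjects (4 doses) it is 98.1% and 97.3%. On average, the conservatism of the exact method in tiny samples roughly offsets the clustering or more, although coverage is lower at particular rates (minimum 88.5% for 6 subjects at r = 0.5).

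**The case against.** The strongest objection is that nothing turns on these rows. They are supplementary. The protocol-planned primary safety analysis (SAP 5.5.1, Table 6) is incidence per group for each dose and overall, and the subject-level percentages use one observation per subject and are valid. Outside the efficacy objectives, "comparative analyses are descriptive with the aim to characterize the difference between groups" (SAP 6). No hypothesis in Protocol 10.1.1 and no holding rule in Protocol 8.6.3 uses these intervals. All of this stands, and it sets the low priority.

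A second objection is that the size is assumed. That also stands: at r = 0.1 the limits at a 30% rate move by only 0.2 points. But the direction under positive correlation does not depend on the assumed value.

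A third is that table layouts sit in a separate document (SAP 10.2), so a footnote there cannot be excluded. The unit and the interval method are nevertheless both stated in the SAP itself.

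Three stronger readings are tempting and are not supported:
- **That every Group 5 dose row covers less than 95%.** Some rows, such as grade 3 reactions, may be rare, and the rare-event figures include several above 95%.
- **That the Group 4 intervals are generally too narrow.** Mean coverage there is near or above 95% at r of 0.3 to 0.5.
- **That a dose-level interval narrower than a single-dose subject interval is itself an error.** It uses more data and should be narrower; the fault is only the part of the narrowing that clustering does not justify.

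**Conclusion.** The point holds for the pooled percentage-of-doses rows in Group 5. As written, the SAP applies an independent-trials method to up to two doses per subject, and the interval is too narrow if the two reactions are positively correlated. For reactions with rates of about 5% or more, equal at both doses, in an arm of 250 with both doses documented, the shortfall from nominal coverage is at most about 1 percentage point at correlation 0.1, about 2-3 at 0.3 and about 4-5 at 0.5. It is smaller when second doses are missing or the rates differ between doses. For rarer reactions no general statement about undercoverage is possible. Groups 1-3, which receive one dose, and all subject-level intervals are unaffected. This is worth correcting because it is cheap, not because any conclusion depends on it.

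**What to change.** Add one sentence to SAP 5.5.2.1 or 10.1.5.1: Group 5 percentages of doses are shown without a confidence interval, or with one clustered on subject, and Clopper-Pearson is kept for all subject-level percentages.

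If an interval is kept, one workable form is Clopper-Pearson on the number of doses divided by the estimated design effect. That effect is the subject-clustered variance of the percentage over its binomial variance, floored at 1. Plain Clopper-Pearson is used when no dose or every dose has the event, because the design effect is then undefined. In simulations with 250 subjects (200,000 per setting, rates of 1-60%, correlations 0 to 0.7) its coverage ran from 94.8% to 98.1%.

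Omitting the interval from the Group 4 dose rows is optional, for consistency; an estimated design effect is unreliable with 6 or 2 subjects.

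The cost is slightly wider or missing intervals in supplementary rows and a small edit to the table layouts or program. Sample size, alpha and point estimates do not change.

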5.5.2.2. Analysis of unsolicited AEs, SAE and pIMD

The analysis of unsolicited AEs will be performed on the Unsolicited safety set.

All the unsolicited adverse events occurring during the study, judged either as related or not related to vaccination by the investigator, will be recorded.

The original verbatim terms used by investigators to identify adverse events in the e-CRFs will be mapped to preferred terms using the MedDRA dictionary. The unsolicited adverse events will then be grouped by MedDRA preferred terms into frequency tables according to system organ class. Adverse events judged by the investigator as at least possibly related to study vaccine will be summarized by vaccine group, according to System Organ Class (SOC) and Preferred Term (PT) within SOC. When an unsolicited adverse event occurs more than once for a subject, the maximal severity and strongest relationship to the vaccine group will be counted (specifically, for dose-escalation safety lead-in).

The percentage of subjects with at least one report of unsolicited AE classified by the MedDRA during a 30-day follow-up period after each dose (i.e. day of injection and the 29 subsequent days) will be tabulated with exact 95% CI for each group. The same tabulation will be performed by severity, by vaccination and for unsolicited AEs with a relationship to vaccination.

SAEs, deaths, pIMDs and AEs leading to withdrawal reported during the entire study will be tabulated (from Day 1 until study termination) and listed.

In addition, SAEs related to study participation or concurrent GSK medication/vaccine reported from inform consent signed until entire study duration will be also listed.

Incidence of COVID-19 reported as an unsolicited AE and SAE will be tabulated with exact 95% CI for each group.

A summary of COVID-19 assessments throughout the study will be tabulated for each group.

This study foresees one injection in groups 1-3 and two injections (i.e., two vaccinations) for each subject in groups 4 and 5, and thus unsolicited AEs summary tables will be presented overall and by period of onset and will include frequency distributions of the different adverse events.

Number and percentage of subjects with the following AEs will be computed:

Onset between the day of each injection and the 29 subsequent days after each vaccination:

- Any AE (overall)
- Any AE by vaccination
- Any AE by severity (overall) (only Grade 3 severity for dose-escalation safety leadin)
- Any AE by severity and by vaccination (PoP only)
- Related unsolicited AEs (overall)
- Related unsolicited AEs by vaccination
- Related unsolicited AEs by severity (overall) (only Grade 3 severity for doseescalation safety lead-in)
- Related unsolicited AEs by severity and vaccination (PoP only)
- Any medically attended unsolicited AE (overall)
- Any medically attended unsolicited AE, by vaccination
- Any related AE with onset within 7 days from vaccination with the PT code in Table 9

Onset between the Day of injection (Day 1) and Day 366 for the Groups 1-3, Day 1 and Day 426 for the Groups 4 and 5

- Any serious adverse events (SAE) (overall)
- Any serious adverse events (SAE) by vaccination
- Any serious adverse events (SAE) by severity (only Grade 3 severity for doseescalation safety lead-in)
- Related SAE (overall)
- Related SAE by vaccination
- Related SAE by severity (only Grade 3 severity for dose-escalation safety lead-in)
- Any AE leading to death (overall)
- Any unsolicited AE leading to premature withdrawal from study (overall)
- Any potential immune mediated diseases (overall)
- Any potential immune mediated diseases by vaccination
- Any AE leading to hospitalization (overall)

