# 12.5.8.1. Time period for detecting and recording adverse events, serious adverse events and pregnancies

All solicited AEs during 7 days following administration of each dose of study vaccine(s) (Day 1 to Day 7 and Day 61 to Day 67) must be recorded in the eDiary, irrespective of intensity or whether or not they are considered vaccination-related.

All other AEs during 30 days following administration of each dose of study vaccine(s) (Day 1 to Day 30 and Day 61 to Day 90) must be recorded in the appropriate section of the eCRF, irrespective of intensity or whether or not they are considered vaccination-related.

The time period for collecting and recording SAEs will begin at the first receipt of study vaccine(s) and will end 366 days following administration of the last dose of study vaccine(s) for each subject (i.e. the last study visit for each subject). See Section 12.5.9 for instructions on reporting of SAEs. However, any SAEs assessed as related to study participation (e.g. study treatment, protocol-mandated procedures, invasive tests, or change in existing therapy) or related to a GSK product will be recorded from the time a subject consent to participate in the study.

All AEs/SAEs leading to withdrawal from the study will be collected and recorded from the time of the first receipt of study vaccine(s).

In addition to the above-mentioned reporting requirements and in order to fulfil international reporting obligations, SAEs that are related to study participation (i.e. protocol-mandated procedures, invasive tests, a change from existing therapy) or are related to a concurrent GSK medication/vaccine will be collected and recorded from the time the subject consents to participate in the study until she/he is discharged from the study.

The time period for collecting and recording pregnancies will begin at the first receipt of study vaccine(s) and will end 366 days following administration of the last dose of study vaccine(s) (i.e. the last study visit for each subject). See Section 12.5.9 for instructions on reporting of pregnancies.

The time period for collecting and recording of pIMDs will begin at the first receipt of study vaccine(s) and will end 366 days following administration of the last dose of study vaccine(s) (i.e. the last study visit for each subject). See Section 12.5.9.5 for instructions on reporting of pIMDs.

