10.1.1. Attributing events to vaccine doses

The dose relative to an event is the most recent study dose given to a subject prior to the start of a given event. For example, if the start date of an adverse event is between Dose 1 and Dose 2, the relative dose will be Dose 1.

If an event starts on the same day as a study dose, the relative dose will be derived from the additional information provided in the CRF using the contents of the flag indicating if the event occurred before or after vaccination. If 'after vaccination' is selected, the relative dose for the event will be the one administered on the start day of the event. If 'before vaccination' is selected, the relative dose for the event will be the dose prior to this one. If the flag indicating whether the event occurred before or after vaccination is missing then "after vaccination" is imputed and relative dose is assigned accordingly.

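### The by-dose rows for SAEs and pIMDs set about 60 days after Dose 1 against about 366 days after Dose 2, so crude percentages need person-time beside them

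*SAP*

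**What the plan says.** SAP 5.5.2.2 introduces its lists with "Number and percentage of subjects with the following AEs will be computed". The first list covers unsolicited AEs and uses the same 30-day window after each dose. The second uses one long window, "Day 1 and Day 426 for the Groups 4 and 5", and includes "Any serious adverse events (SAE) by vaccination", the corresponding row for related SAEs, and "Any potential immune mediated diseases by vaccination". Each of the three also has an overall row.

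In this section vaccination means the injection, not the arm: "This study foresees one injection in groups 1-3 and two injections (i.e., two vaccinations) for each subject in groups 4 and 5". Events are allocated to doses by SAP 10.1.1: "The dose relative to an event is the most recent study dose given to a subject prior to the start of a given event". That rule has no upper time limit.

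SAP section 3 places the two doses on Days 1 and 61. Protocol 12.5.8.1 says that collection of SAEs, and likewise of pIMDs, "will end 366 days following administration of the last dose of study" vaccine. Neither document specifies person-time, an exposure-adjusted rate or a shorter window for the three by-vaccination rows, and the SAP does not state their denominator.

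**The concern.** A by-dose safety table in a first-in-human two-dose study invites the question whether the second dose is worse than the first. Here the two dose periods differ about six-fold in length, and a percentage of subjects takes no account of that. SAEs or pIMDs occurring at a steady background rate would appear several times more often after Dose 2 than after Dose 1, in both arms, with no dose effect. In the same rows, a true early excess after Dose 2 would be mixed with about 11 further months of background events.

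SAEs and pIMDs are primary endpoints, and immune-mediated disease is the candidate-vaccine risk named in Protocol 3.3.1, so these rows will be read closely. The unsolicited AE rows in the same SAP section avoid the problem by using equal windows.

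**Working it through.** **Inputs.** Dose days 1 and 61 (SAP section 3). End of window Day 426 (SAP 5.5.2.2). Allowed PoP intervals of 60 to 67 days from Dose 1 to Dose 2 and 365 to 380 days from Dose 2 to the last visit (Protocol Table 6). Planned size about 250 per arm (Protocol Table 11). Event rates are assumptions, because the documents give none.

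**Window lengths, counting days inclusively**
- Dose 2: 426 − 61 + 1 = 366 days, which reproduces the 366 days in Protocol 12.5.8.1.
- Dose 1: 60 − 1 + 1 = 60 days.
- Ratio: 366 / 60 = 6.10.
- Across the allowed intervals: lowest 359 / 67 = 5.36 (Dose 2 on Day 68, cut at Day 426: 426 − 68 + 1 = 359); highest 381 / 60 = 6.35.

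**Percentage with at least one event.** With constant rate r per year and window t days, p = 1 − exp(−r·t/365.25). For subjects with both doses and full follow-up:

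| Assumed rate per year | After Dose 1 (60 d) | After Dose 2 (366 d) | Ratio |
|---|---|---|---|
| 1% | 0.16% | 1.00% | 6.07 |
| 2% | 0.33% | 1.98% | 6.05 |
| 5% | 0.82% | 4.89% | 5.97 |
| 10% | 1.63% | 9.54% | 5.85 |
| 20% | 3.23% | 18.16% | 5.62 |
| 50% | 7.89% | 39.41% | 5.00 |

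At 5% per year and 250 subjects, this is about 2.0 subjects after Dose 1 and 12.2 after Dose 2.

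**Loss to follow-up, at 5% per year.** With yearly loss L and h = −ln(1 − L), counted from the start of each period, the observed proportion is r/(r+h) × [1 − exp(−(r+h)·t/365.25)]. The ratio is 5.72, 5.46 and 5.18 for L = 10%, 20% and 30% (assumed).

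**Subjects with Dose 1 only who stay in follow-up.** Protocol 9.2 allows this, and under SAP 10.1.1 all their events stay with Dose 1. For a share s followed to Day 426, the Dose 1 percentage is (1 − s) × 0.818% + s × [1 − exp(−0.05 × 426/365.25)], where the bracket is 5.665%. At s = 5% this is 0.777% + 0.283% = 1.060%. With Dose 2 recipients as the second denominator, the ratio is 4.887 / 1.060 = 4.61. At s = 10% and 20% (assumed) it is about 3.8 and 2.7.

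**Share of early events in the Dose 2 row.** At 5% per year, 30 days give 1 − exp(−0.05 × 30/365.25) = 0.41%, and 0.41 / 4.89 is about 8%. More than 90% of background cases in that row would have onset after the first 30 days.

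**With the change.** At a constant 5 events per 100 person-years, the rate is 5.0 after each dose, ratio 1.0. Equal 30-day windows give 0.41% after each, ratio 1.0.

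**The case against.** The strongest reply is that nothing planned in the protocol is affected. Protocol 10.3.5 and SAP 5.5.1 plan the number and percentage of subjects with an SAE or pIMD over the whole study, with no split by dose. The by-dose rows appear only under the SAP's additional considerations. SAP section 6 makes the non-efficacy comparisons descriptive and between groups, and no test of Dose 2 against Dose 1 is planned. Both arms share one schedule, so the placebo arm would show the same rise. All of this stands.

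A reader might therefore infer too much in three ways.
- *That the primary safety analysis or the vaccine-placebo contrast is biased.* It is not, because within each dose period the arms have the same nominal window.
- *That a six-fold rise is certain.* Six is near the upper end. It needs low constant rates, both doses and full follow-up. For related SAEs it is not shown, because causality assessment should remove much of the background.
- *That early events after Dose 2 are lost.* SAP 10.1.2.4 includes SAEs in the unsolicited AE summaries, so SAEs starting within 30 days of a dose are already in equal-window tables. SAEs and pIMDs are also listed individually, and onset day is derived from the last vaccination (SAP 10.1.3.6). The 30-day tables do not show SAEs separately, however, so this covers the gap only in part.

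Table layouts are held in a separate document (SAP 10.2) and may give denominators or period lengths. The SAP itself does not.

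**Conclusion.** The concern holds as one of interpretability. For two-dose completers, the by-dose SAE and pIMD rows rest on about 60 days against about 366 days, a ratio that follows directly from the documents' schedule and attribution rule. The crude percentage after Dose 2 would be about six times as high as after Dose 1 at a low constant rate with no dose effect. Under the assumed dropout and Dose-1-only scenarios above, the ratio ranges from about 5.7 down to 2.7. A reader could not correct for it by dividing by a fixed factor, because Dose-1-only follow-up changes the Dose 1 period.

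The point applies to Groups 4 and 5 only. In practice that means Group 5, since Group 4 has eight subjects and Groups 1 to 3 receive one dose. It applies less clearly to related SAEs. It does not touch the overall tables or the comparison between arms, so the change is recommended for clear reading of the by-dose rows rather than to protect a planned inference.

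**What to change.** In SAP 5.5.2.2, for the SAE, related SAE and pIMD rows by vaccination, report for each dose and arm the number of subjects with an event, the person-time at risk and the rate per 100 person-years. Define person-time from each dose to the earliest of the next dose, the first such event in that period, last contact, or the end of the Day 1 to Day 426 window, in line with SAP 10.1.1. State the denominator. Keep the crude Day 1 to Day 426 percentages for the overall rows.

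Optionally, add a row for onset within the existing 30-day window after each dose, so that early SAEs and pIMDs can be seen separately. This should supplement the rates and not replace them, because used alone it would drop later-onset pIMDs from every by-dose display.

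The cost is SAP wording, slightly more programming and three changed table shells. No new data are needed.
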